**by the Icahn School of Medicine at**  
**Mount Sinai (ISMMS) Institutional**  
**Review Board (IRB) Under a**  
**Different Principal Investigator**

---

**Protocol Was Previously Submitted** No  

**Other External Site Name**

**Contact Details**

**Approved**

**Approval Document**

**Funded By Mount Sinai**

**Other IRB**

**6. Subjects - Enrollment**

**Site Name** Icahn School of Medicine at Mount Sinai  
**Subjects To Be Enrolled** 20  
**Total Number of Subjects to be Enrolled Across All Listed Sites Above (Auto Populated)** 20

## **7. Subjects - Setting and Resources**

**Setting of Human Research** Other

**Specify Other Setting of Human Research**

Seaver Autism Center for Research and Treatment at Icahn School of Medicine at Mount Sinai

**Total Number of Subjects Needed** 20

**To Complete Study**

**Feasibility of Meeting Recruitment Goals**

Power is calculated for differences in baseline to week 12 change scores. Testing for treatment x time interactions and # at .05, we have 80% power to detect moderate to large effects.

Based on data from our previous clinical trial of IGF-1 in patients with Phelan McDermid Syndrome, a 12 week study was feasible in 9 patients.

We feel that 20 patients would provide adequate data to establish the utility of growth hormone in this population. The Seaver Autism Center has access to this population of children with Phelan McDermid Syndrome which should help facilitate recruitment.

**Facilities To Be Used for Conducting Research**

Seaver Autism Center at Icahn School of Medicine

Pediatric Endocrinology & Diabetes Outpatient Clinic at Mount Sinai

---

**Multi-Center Study** No

---

**Community-Based Participant Research Study** No

***PI must attest to the following.***

***\* Process is adequately described to ensure that all persons assisting with the trial are adequately informed about the protocol, the investigational product(s), and their trial-related duties and functions.***

## **8. Subjects - Populations**

### **Inclusion Criteria**

Diagnosis: Pathogenic deletions or mutations of the SHANK3 gene confirmed by array CGH and/or direct sequencing.

Age Range: Cases will be between 2 and 12 years old at the time the phenotypic measures were collected.

### **Exclusion Criteria**

Cases will be excluded if any of the following criteria are applicable:

- closed epiphyses;
- active or suspected neoplasia;
- intracranial hypertension;
- hepatic insufficiency;
- renal insufficiency;
- cardiomegaly/valvulopathy;
- history of allergy to growth hormone or any component of the formulation (mecasermin);
- history of extreme prematurity (<1000 grams) with associated early neo-natal complications, e.g. intra-cerebral hemorrhage, prolonged hypoxia, prolonged hypoglycemia;
- patients with comorbid conditions who are deemed too medically compromised to tolerate the risk of experimental treatment with growth hormone.
- Patient with visual problems that preclude the use of VEPs

**Enrollment Restrictions Based Upon Gender, Pregnancy, Childbearing Potential, or Race** Yes

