### **Safeguards to protect Subjects rights and welfare**

Participants suitable for the study will undergo comprehensive medical evaluation by the study psychiatrist. Medical history, family history, physical and neurological examination (including anthropometric measurements, fundoscopic exams), routine hematology and blood chemistry (including liver profile) and X-ray will be performed at baseline.

Patients will be monitored for tolerability every 4 weeks throughout the study using physical and neurological examination (including anthropometric measurements and fundoscopic exams). Patients will be monitored at weeks 4, 8, and 12 and then again 4-weeks after study termination with the following safety measures: physical and neurological examination (including anthropometric measurements and fundoscopic exams), routine hematology and blood chemistry.

Potential adverse events from Growth Hormone (GH) will be explained to participant's families and also be monitored for during their serial evaluations.

Informed consent shall be obtained from parents or legal guardians after a thorough explanation of the study protocol.

The study will be conducted according to Good Clinical Practice (GCP), the 1996 Declaration of Helsinki (Protocol Appendix A), (US 21 CFR Part 50—Protection of Human Subjects, and Park 56—Institutional Review Boards) and local rules and regulations of the country.

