### **Drug**

Growth hormone is secreted by the somatotrophs of the anterior pituitary gland in a pulsatile manner. It binds to its receptor, signaling a cascade of intracellular events which directly stimulated the synthesis and release of IGF-1. (Ashpole et al; 2014, Grimberg et al; 2016).

Growth hormone is FDA approved for use in children with growth hormone deficiency (including idiopathic [of unknown cause] growth hormone deficiency), Turner syndrome, Noonan syndrome, Prader-Willi syndrome, short stature homeobox-containing gene (SHOX) deficiency, chronic renal insufficiency, idiopathic short stature and children small for gestational age. (<https://www.fda.gov/Drugs/DrugSafety/ucm237839.htm>)

It is available in the form of several commercial preparations. This is typically available as a 10 mg vial to be reconstituted with in-package syringe of 1 mL of bacteriostatic water (preserved with 0.33% metacresol), and a 25G reconstitution needle.

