### **Drug Administration**

Growth hormone will be administered subcutaneously once daily using a 12-week single group design. No placebo will be used. The 12-week duration was selected because of our previous trial with IGF-1 showing effects in standardized behavior scales in that duration, hence establishing proof of concept.

The dose of daily growth hormone varies with the indication for therapy. Approved doses of growth hormone range from 0.16-0.25mg/kg/week for growth hormone deficient patients (Grimberg et al.; 2016) and up to 0.47 mg/kg/week for patients born small for gestational age.

In our proposed trial, we expect a majority of our patients to be growth hormone sufficient and therefore similar to the population of children with idiopathic short stature treated with growth hormone. We will recommend a dose of 0.15mg/kg/week divided daily for 2 weeks as a starting dose to ensure safety and tolerance. The dose will then be increased to 0.3mg/kg/week for 10 weeks, an average growth hormone dose in children with idiopathic short stature.

The growth hormone dose will be titrated based on IGF-1 levels monitored serially up to a maximum dose of 0.45mg/kg/week. (<http://www.ferringusa.com/wp-content/uploads/2018/07/ZOMACTON-PI-7-18.pdf> )

Drug dose is calculated on a mg/kg/week basis. Using Center for Disease Control average Weight-for-age statistics in typically developing children ages 2 to 12 years ([www.cdc.gov/growthcharts/cdc\\_charts.htm](http://www.cdc.gov/growthcharts/cdc_charts.htm)), the overall average weight across a representative sample of males and females in this age range is 24.65kg.

Average growth hormone dose for weeks 1-2: 0.15mg \* 24.65kg per week = 3.7 mg per week

Average growth hormone dose for weeks 3-10: 0.3mg \* 24.65kg per week = 7.4 mg per week

With a recruitment target of 20 patients, we anticipate the need for a total of 1628 mg of growth hormone with each person requiring about 81 mg of growth hormone in 12 weeks. We anticipate the need for 17 vials of growth hormone (10 mg per vial).

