## **25. Drugs / Biologics**

Study Fund Account (or alternate departmental / fund account, if study is not yet established)	[REDACTED]
Generic Name	Recombinant Human Growth Hormone (Somatropin)
Brand Name	Uncertain at this point
Drug Has Valid IND	No
	For each drug / biologic with an IND number, ensure that the application includes one of the following. * Sponsor protocol with the IND number. * Communication from the sponsor or the FDA with the IND number.
IND Number	
Name of IND Holder	
Type of IND Holder	
Drug Meets One of the Following Categories for Exemption	Yes
	
Category 1: * The drug is lawfully marketed in the United States. * The research is not intended to be reported to the FDA as a well-controlled study in support of a new indication for use nor intended to be used to support any other significant change in the labeling for the drug. * The research is not intended to support a significant change in the advertising for the product. * The research does not involve a route of administration or dosage level or use in a patient population or other factor that significantly increases the risks (or decreases the acceptability of the risks) associated with the use of the drug. * The research is conducted in compliance with the marketing limitations described in 21 CFR §312.7. Category 2: * A clinical investigation for an in vitro diagnostic biological product that involves one or more of the following: (1) Blood grouping serum; (2) Reagent red blood cells; or (3) Anti-human globulin. * The diagnostic test is intended to be used in a diagnostic procedure that confirms the diagnosis made by another, medically established, diagnostic product or procedure. * The diagnostic test is shipped in compliance with 21 CFR §312.160. Category 3: * A clinical investigation involving use of a placebo when the investigation does not otherwise require submission of an IND.

Category for Exemption	Category 1

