Drug / Biologic Description (Manufacturer/Generic Name/Form/Strength)	Somatropin/recombinant Human Growth Hormone as a subcutaneous injection, typically sold commercially as 10mg/vial
Controlled Substance Schedule	No
Using Investigational Drug Service (IDS) Research License	In order for the Icahn School of Medicine at Mount Sinai (ISMMS) to be compliant with the regulations regarding controlled substance research, a New York State Department of Health-issued Researcher license and DEA-issued Researcher Registration Number must be on file for each trial using controlled substances. The Investigational Drug Service maintains these licences and will make them available to our investigators to support our research. Refer to www.health.state.ny.us/professionals/narcotic and http://firstclinical.com/journal/2011/1112_DEA.pdf for more information.
Use of this Drug / Biologic Is Considered Standard of Care	No
Requested Pharmacy Services	Dispensation, Storage, Label
Specify Other Requested Pharmacy Services	
Drug / Biologic Will Be Supplied By	Commercially Available/Sourced by Hospital
Specify Other Drug / Biologic Supplier	
Using Placebo	No
Placebo Will Be Supplied By	
Compounding Required (Paid for by Study Funds)	
Where Drug / Biologic Will Be Administered	Outpatient Clinic
Specify Location of Private Office	
Storage Requirements of Drug / Biologic	Refrigerated (2-8°C)
Where Drug / Biologic Will Be Stored	Patients Own Supply
ALL of the Following Storage Criteria Are Met	

\* The storage area is well maintained, provides adequate lighting, ventilation, sanitation, space and security. \* The temperature in the storage area is controlled and monitored using calibrated monitoring devices. \* The temperature monitoring system has sensors

for continuous monitoring and alarms set at the points representing the temperature extremes. \* Records of temperatures and alarms are maintained and all excursions outside the labeled storage conditions are appropriately investigated and reported to the sponsor.

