**27. Attachments**

Type	Name	Version	Status	Filename	Uploaded Date
FDA - Package Insert for Approved Drug	Package Insert for Zomacton	1	New	ZOMACTON Somatropin Package insert.pdf	11/14/2018
FDA - Other Materials	[name] IGF-1 trial performed at ISMMS	1	New	IGF-1 in PMS clinical trial.[name].pdf	11/14/2018
Consent Documents	GH consent.docx	1	New	GH Consent version date 02-26-19.docx	02/26/2019
Data Collection Sheet	DATA COLLECTION SHEET edited.docx	1	New	DATA COLLECTION SHEET edited.docx	11/15/2018
Other - Other IRB Correspondance	Research Plan PDF.pdf	1	New	Research Plan PDF 12.3.18.pdf	12/03/2018
Parental Permission Document	GH consent.docx	1	New	GH Consent version date 02-26-19.docx	02/27/2019
Data Monitoring Committee Description	Data Monitoring Committee.docx	1	New	Data Monitoring Committee.docx	11/15/2018
Package Insert Document (DRUG NAME)	ZOMACTON Somatropin Package insert.pdf	1	New	ZOMACTON Somatropin Package insert.pdf	11/15/2018
Advertisement - Website text/Screen shots/URLs	Ad for websites	1	New	Ad.docx	12/03/2018
Dosimetry Chart	DOSIMETRY.xlsx	1	New	DOSIMETRY.xlsx	01/17/2019
Other - Other IRB Correspondance	Correspondance regarding dosimetry	1	New	Radiation dosimetry correspondance.pdf	01/17/2019
FDA - FDA or Manufacturer Risk Determination	FDA IND exemption	1	New	FDA IND exemption.pdf	02/06/2019

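### The allergy exclusion names the formulation as mecasermin, but the only drug given is somatropin, so its component clause, read literally, points to the wrong product.

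*Combined protocol and SAP*

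**What the plan says.** The list under Exclusion Criteria in section 8 (Subjects - Populations) includes a "history of allergy to growth hormone or any component of the formulation (mecasermin", where the bracket closes after that word. The list is repeated with the same allergy wording in section 12 (Procedures - Narrative), under Description of the Study Design.

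On what the children are given, section 12 (Drug Administration) says: "Growth hormone will be administered subcutaneously once daily using a 12-week single group design. No placebo will be used". Section 25 (Drugs / Biologics) gives the generic name as "Recombinant Human Growth Hormone (Somatropin") and the brand as "Uncertain at this point". It describes the product as "Human Growth Hormone as a subcutaneous injection, typically sold commercially as 10mg/vial". The package insert listed in section 27 (Attachments) is "ZOMACTON Somatropin Package insert.pdf".

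Section 12 (Drug) describes the usual presentation as a vial reconstituted with "bacteriostatic water (preserved with 0.33% metacresol").

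**The concern.** The bracket reads as a gloss on the formulation: it tells the screener which product's components to ask about. The product it names is not the one being injected. Since there is a single treatment group and no placebo, there is no second product to which the bracket could properly refer.

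This is an operative safety rule, so it should name the right product. Two errors in screening are conceivable:

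- A child allergic to a component of the somatropin product, but not of mecasermin, would pass this criterion.
- A child allergic only to a component of mecasermin would be turned away without reason, in a trial that seeks just 20 children with a rare condition.

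Both are assumptions. Each requires the two products to differ in their components, and the documents do not show whether they do.

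**Working it through.** No figure in the plan bears on this point, so there is nothing to recompute. The check is a comparison of text.

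**Step 1: where the word occurs.** Mecasermin occurs 2 times in the document, once in each copy of the allergy criterion (sections 8 and 12). It is not defined, its components are not listed, and it is not named as a study drug anywhere.

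**Step 2: what is given.**

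| Place | Product |
|---|---|
| Section 8, Exclusion Criteria | formulation glossed as mecasermin |
| Section 12, Description of the Study Design | formulation glossed as mecasermin |
| Section 12, Drug Administration | growth hormone only, no placebo |
| Section 25, generic name | somatropin |
| Section 25, drug description | somatropin, 10 mg vial |
| Section 27, package insert | a somatropin product |

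The brand is undecided, but the generic drug is fixed. Whichever brand is chosen, it will be a somatropin product, so the open brand does not rescue the bracket.

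**Step 3: what the criterion still covers.** It has two parts. The first, allergy to growth hormone, is correct and covers the active substance. Only the second, on components, is misdirected.

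**Step 4: whether another rule fills the gap.** Each list has 10 exclusions, and 1 concerns allergy. Of the remaining 10 − 1 = 9, none mentions allergy to an excipient or diluent. The nearest lets the investigator exclude a child whose other medical conditions make the experimental treatment too risky. That is a matter of judgement and does not direct anyone to ask about components. The text on how participants will be screened (section 9) refers to the inclusion criteria, the diagnosis and open epiphyses, and does not mention allergy. A baseline work-up is planned in section 8: "Participants suitable for the study will undergo comprehensive medical evaluation by the study psychiatrist". It includes a medical history, which could bring an allergy to light but sets no rule for exclusion.

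**Step 5: whether the component clause has any content here.** It does. The protocol names one non-active component, metacresol in the diluent, but only as part of the typical presentation. Whether the supplied brand will contain it is not settled.

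**Step 6: size.** The error affects 1 of 10 listed criteria, appears in both copies of the list, and applies to all 20 planned children. These counts describe the reach of the text. They do not measure harm.

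**The case against.** The strongest reply is that the criterion works despite the bracket. In a protocol with one drug and no placebo, the formulation most naturally means the growth hormone product being injected, and a sensible screener would treat the bracketed word as a slip. The documents identify no component that would be missed and no child who would be wrongly excluded. The discretionary exclusion for medical conditions, the baseline history, the attached somatropin insert, the investigator's power to withdraw a child, and the default to withdrawal when safety is in doubt all reduce the consequence. Some attachments, such as the research plan and the data collection sheet, are not available for reading and might word eligibility correctly.

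Most of this stands as an argument about size. A screener probably would read past the slip, and harm is not shown. It does not make the text right. An eligibility rule should not depend on staff disregarding the product it names. The withdrawal provisions act only after enrolment, and the baseline history collects information without saying what to do with it. Correct wording in an attachment would leave the protocol at odds with it.

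The wrong name could have been carried over from another protocol. The descriptions of some outcome measures in section 12 refer to FXTAS, which is not the condition under study. That explanation is an inference, and the conclusion does not depend on it.

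**Conclusion.** The point holds and is minor. The component part of the allergy exclusion names a product that is not given in this trial, in both places where the list appears, and nothing else in the document corrects it. That conclusion rests only on the text and is held with high confidence. It does not require knowing what mecasermin contains.

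The practical consequence is much less certain. Any effect on a child requires that the two products differ in a component, that a child is allergic to it, and that the screener follows the bracket literally. The documents give no figure for any of these. The number affected cannot be estimated and may be zero.

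**What to change.** In section 8 (Exclusion Criteria) and section 12 (Description of the Study Design), replace the bracketed word with wording such as: the somatropin product supplied, including its excipients and diluent preservative, for example metacresol if present. Use the same wording wherever eligibility is recorded, and check it against the package insert once the brand is fixed.

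The cost is one phrase changed in two places, plus any matching eligibility form. Sample size, endpoints, analysis and stopping rules are untouched.

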**Upon Gender, Pregnancy, Childbearing Potential, or Race**

### **Justify Restriction(s)**

We will only recruit children between 2 to 12yrs of age and pregnant women will be excluded from the study since this is a pilot clinical trial of GH in children with Phelan McDermid Syndrome.

**Age Range(s)** Newborn to 8 Years, 9 to 17 Years

**Targeted Population(s)** Children

**Individuals Under 18 Consenting for Themselves Under NYS Law?** No

***In most cases this does not apply. Typically subjects under 18 assent and a parent (or two) consents for the subject to be in research. This is only for very limited scenarios where the study is related to services/treatment (usually limited to reproductive health, substance abuse or mental health issues) that those under 18 can obtain without parental involvement in NYS and where there was no parental involvement for the related clinical services. See SOP-013 (point 3.2) for additional information.***

### **Other Aspects that Could Increase Subjects Vulnerability**

Informed consent shall be obtained from parents or legal guardians of patients with Phelan McDermid Syndrome who typically have global developmental delays and are cognitively impaired.

### **Safeguards to protect Subjects rights and welfare**

Participants suitable for the study will undergo comprehensive medical evaluation by the study psychiatrist. Medical history, family history, physical and neurological examination (including anthropometric measurements, fundoscopic exams), routine hematology and blood chemistry (including liver profile) and X-ray will be performed at baseline.

Patients will be monitored for tolerability every 4 weeks throughout the study using physical and neurological examination (including anthropometric measurements and fundoscopic exams). Patients will be monitored at weeks 4, 8, and 12 and then again 4-weeks after study termination with the following safety measures: physical and neurological examination (including anthropometric measurements and fundoscopic exams), routine hematology and blood chemistry.

Potential adverse events from Growth Hormone (GH) will be explained to participant's families and also be monitored for during their serial evaluations.

Informed consent shall be obtained from parents or legal guardians after a thorough explanation of the study protocol.

The study will be conducted according to Good Clinical Practice (GCP), the 1996 Declaration of Helsinki (Protocol Appendix A), (US 21 CFR Part 50—Protection of Human Subjects, and Park 56—Institutional Review Boards) and local rules and regulations of the country.

## **9. Subjects - Participation**

### **Duration of an Individual Subjects Participation in the Study**

Approximately 6 months or lesser

### **Duration Anticipated to Enroll All Study Subjects**

15 months

**Estimated Date for the Investigators** Within two years to Complete This Study

### **Procedures for Subjects to Request Withdrawal**

Indications to halt active participation of the subject in the GH study

1. Withdrawal of Consent : Patient families may withdraw consent at any time during the course of the study.

To avoid bias, all analyses will include all subjects, including those withdrawn from the study, regardless of adherence to study protocol. If there is doubt concerning a subject's safety, the default mode must be withdrawal from treatment or active study participation, followed by close observation (safety follow up visits) and recommendation of standard treatment.

Return of a subject to active study participation will not be permitted, except if a transient clinical or laboratory abnormality unrelated to study treatment has occurred and subsequent permission to return the patient to active study has been provided.

If a subject is withdrawn from active study during Growth Hormone treatment, they will be returned to the referring physician and standard care will be recommended; in addition, we will request the subject's participation in an end-of-study visit.

